3.1 STUDY SUCCESS AND TEST OF THE STUDY'S PRIMARY HYPOTHESIS

This study is designed to show that the investigational device (Cementless) is non-inferior to the Control device using four co-primary study endpoints. This will be shown using a closed testing method in which each of the primary endpoints specified above are compared using α =0.05. Study success requires that the Cementless group successfully demonstrate non-inferiority when compared to the Control group for all four of the individual primary endpoints, using the statistical methods described below. Because non-inferiority must be successfully shown for all four endpoints for study success, the type I error rate is preserved at 5% for the entire primary endpoint.^b The individual non-inferiority hypotheses for each of these four tests are as follows:

3.1.1. RADIOGRAPHIC SUCCESS

The proportion of radiographically successful knees in the Cementless group is non-inferior to the proportion of radiographically successful knees in the Control group using an 8% margin of non-inferiority. The test is based on the upper bound of a one-sided 95% confidence interval for the difference, Control minus Cementless, of proportions of success at 22+ months. A conclusion of non-inferiority is supported if the upper bound of the confidence interval is 0.08 or less. In addition, a Fisher's Exact p-value will also be computed to test this hypothesis.

In this analysis, each knee will be considered as a separate case, and unilateral and bilateral subjects will be analyzed together, providing the unilateral and bilateral groups are poolable per sensitivity analyses given in Section 3.1.5°.

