- 24. Patients who have received systemic steroids within the past 6 months or steroid injection into the affected knee within the previous 6 weeks prior to enrollment
- 25. Patients who are pregnant
- 26. Patients with severe valgus or varus knees (valgus or varus angulation of more than 20°) where collateral ligament, iliotibial band, or popliteal release is required
- 27. Patients who refuse to sign the IRB approved Informed Consent Form
- 28. Participation in an interventional clinical research study procedure, *other than a bilateral knee arthroplasty in this study*, within the past 12 months
- 29. Patients with a history of osteomyelitis or sepsis of the index knee
- 30. Patients who require patellar resurfacing
- 31. Patients who are not skeletally mature
- 32. Patients who have had a total hip replacement procedure <18 months prior to entering the study
- 33. Patients who have had a contralateral non-study knee replacement procedure <18 months prior to entering the study
- 34. Patients who are found intraoperatively to have inadequate bone stock or other conditions that contraindicate a partial knee replacement

NOTE: Patients implanted on the contralateral knee with the investigational or control device as part of their participation in the study are permitted to be enrolled in the study, but will receive a matching device to the original study knee and will not be randomized.

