3.0 STATISTICAL ANALYSIS PLAN

This is a two-group, multi-center, randomized clinical trial to compare Biomet's cemented Oxford® Partial Knee System to another active intervention, the Oxford® Cementless Partial Knee System (abbreviations: Control vs. Cementless). Imbalanced, blocked randomization (2:1, Cementless vs. Control) will be implemented.

Randomization will be per patient. In the event that an intraoperative screen failure occurs post-randomization, randomization will not be reassigned and this patient will not count toward the overall sample size. Randomization will continue with the next subject enrolled as previously described. The randomization plan will be produced using SAS v 9.2 for Windows. Randomization will be by center, and each site will receive separate randomization plans using a predetermined block size that will remain undisclosed to the sites. The randomization assignments will be in the form of envelopes to be opened intra-operatively after the first tibial cut and bone quality is assessed against the eligibility criteria.

The primary study endpoint will consist of four (4) individual co-primary endpoints, including both safety and efficacy measures. The following endpoints are included as individual parts of the primary endpoint:

- 1. Knee Society Assessment Score number of points received for the Knee Society Assessment Score at the 22+ month assessment
- 2. Knee Society Function Score number of points received for the Function Score at the 22+ month assessment.
- 3. Revisions or removals of any component of the device or an unanticipated, device-related adverse event (UADE) at any time point. This is a binary endpoint in which a knee is either a "success" or "failure". To obtain a successful result, a knee must reach the 22 + month upper window limit with the device intact and without a component revision/removal or a UADE.
- 4. Radiographic Assessments at the 22+ month assessment

This is a binary endpoint in which a knee is either a "success" or "failure". To obtain a successful radiographic endpoint, a knee must meet the following criteria at the 22+ month

- a. Absence of osteolysis
- b. No migration/subsidence of any femoral or tibial component
- c. Absence of fractured component

Conversely, a radiographic failure is defined as follows:

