3.1.2. ABSENCE OF REVSION/REMOVAL/UADE

Using a 10% margin of non-inferiority, the proportion of knees who are free of Revision/Removal/UADE during the course of the study in the Cementless group is non-inferior to the proportion of such knees in the Control group. The test is based on the upper bound of a one-sided 95% confidence interval for the difference, Control minus Cementless, of success proportions. A conclusion of non-inferiority is supported if the upper bound of the confidence interval is 0.10 or less. In addition, a Fisher's Exact p-value will also be computed to test this hypothesis.

^b Dmitrienko, Alex, et al. *Analysis of Clinical Trials Using SAS*. SAS Publishing, 2005, pp 75-76.

^c As agreed at FDA pre-submission meeting Q160425 April 13, 2016.

In this analysis, each knee will be considered as a separate case, and unilateral and bilateral subjects will be analyzed together, providing the unilateral and bilateral groups are poolable per sensitivity analyses given in Section 3.1.5^d.

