3.1.5. SENSITIVITY ANALYSES - UNILATERAL AND BILATERAL KNEES

To address the impact of possible correlation occurring due to including two knees from the same patient, for the two endpoints that will incorporate bilateral knees (Radiographic Success and Absence of Revision/Removal/UADE), additional sensitivity analysis will be conducted in order to address any potential correlation occurring due to including two knees from the same patient. These are to include:

- a. An analysis that considers only unilateral subjects.
- b. A repeated measures model approach that can account for possible correlation within subjects.
- c. An analysis of data at the patient level, in which a patient is considered a "failure" if either knee fails.

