3.2. CALCULATION OF THE PRIMARY STUDY ENDPOINT

The confidence intervals used in the analysis of the binary primary endpoints (Radiographic Success and Absence of Revision/UADE) will be 1-sided, 95% confidence intervals for the difference between proportions in two independent samples. They will be calculated using the Wald method as based on a normal approximation to the binomial, as follows:

$$(p_C - p_I) + z_\alpha \sqrt{SE_C^2 + SE_I^2}$$

Where

^d As agreed at FDA pre-submission meeting **Q160425** April 13, 2016.

 p_C = proportion of success in the Control group,

p_I = proportion of success in the Investigational group,

 $\alpha = 0.05$, and

$$SE_C = \sqrt{\frac{p_C(1-p_C)}{n_C}}$$
 and $SE_I = \sqrt{\frac{p_I(1-p_I)}{n_I}}$

The confidence interval used in the analysis of the continuous primary endpoints (Knee Society Function and Assessment Scores) will be 95% confidence intervals for the difference between means in two independent samples. They will be calculated using the normal distribution, as follows:

$$(\bar{x}_C - \bar{x}_I) + z_\alpha \sqrt{\frac{s_C^2}{n_C} + \frac{s_I^2}{n_I}}$$

Where

 $\overline{x_C}$ = proportion of success in the Control group,

 $\overline{x_i}$ = proportion of success in the Investigational group,

 s_C = standard deviation for the Control group,

 s_{I} = standard deviation for the Investigational group,

and

 $\alpha = 0.05$

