Type I error: conclude that the difference p_C - p_I is less than δ when in fact the difference is greater than or equal to δ , *i.e.* conclude that the experimental treatment is non-inferior to the control treatment when the control treatment is actually substantially better.

Statistics in Medicine 9(1990) pp 1447-1454.

^eFarrington and Manning

[&]quot;Test statistics and sample size formulae for comparative binomial trials with null hypotheses of non-zero risk difference for non-unity relative risk".

Type II error: conclude that the difference is greater than or equal to δ when it is actually less than δ , *i.e.*, conclude that the experimental treatment is inferior to the control treatment when the experimental treatment is essentially just as good.

Assumptions:

$\alpha = 0.05$	Probability of Type I error
$\beta = 0.90$	Probability of Type II error: power = $1 - \beta$
$p_{C} = p_I = 0.95$	Estimated success rate for control and treatment groups
δ = 0.08	Non-inferiority Margin

Resulting sample sizes (number of knees), not adjusted for attrition, are 191 Cementless device vs. 96 Control (5% type I error rate, 90% power). We increase our sample size by 10% to allow for possible exclusions in the primary analysis due to bilateral patients who may not be poolable with the unilateral cases, as well as attrition of up to 15%. This gives a sample size of 383 total subjects (255 Cementless vs. 128 Control).

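### For the two binary co-primary endpoints the deciding confidence bound treats both knees of a patient as independent; the effect on type I error is modest, and the variance should be clustered by patient

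*Combined protocol and SAP*

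**What the plan says.** Section 3.0: "Randomization will be per patient". The note that closes section 2.2 adds that a patient whose other knee later enters the study "will receive a matching device to the original study knee and will not be randomized". Both study knees of a patient therefore lie in the same arm.

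For Radiographic Success (3.1.1, margin 0.08) each knee is "considered as a separate case, and unilateral and bilateral subjects will be analyzed together, providing the unilateral and bilateral groups are poolable". Section 3.1.2 (margin 0.10) counts knees in the same way, again "providing the unilateral and bilateral groups are poolable per sensitivity analyses given in Section 3.1.5". In both, the conclusion rests on the upper limit of a one-sided 95% interval for Control minus Cementless. Of these intervals section 3.2 says: "They will be calculated using the Wald method as based on a normal approximation to the binomial". Its formula takes p(1-p)/n in each arm, for two independent samples.

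Section 3.1.5 recognizes the issue: "additional sensitivity analysis will be conducted in order to address any potential correlation occurring due to including two knees from the same patient". It lists (a) unilateral subjects only, (b) a repeated measures model and (c) a patient-level analysis. It gives no statistic, level or consequence for poolability. Section 3.3 adds 10% to the sample size for "possible exclusions in the primary analysis due to bilateral patients who may not be poolable with the unilateral cases", which only implies what would follow. Section 3.5.2 says that bilateral patients enter these two analyses and does not repeat the condition.

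Sections 3.1.1 and 3.1.2 also say that a Fisher's exact p-value will test the stated hypothesis, which is non-inferiority with a margin. Section 3.1 states that, because all four endpoints must succeed, "the type I error rate is preserved at 5% for the entire primary endpoint".

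**The concern.** Two knees of one patient share the patient, and here the device. If their outcomes are positively correlated, the variance of the pooled proportion exceeds p(1-p)/n, the upper bound is too low, and non-inferiority is declared too often. Requiring all four endpoints to pass protects the 5% level only if each component test holds 5%.

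The analyses in 3.1.5 that could deal with this have no stated part in the decision. Whenever knees are pooled, the deciding standard error is the one in 3.2, without a patient term.

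A smaller matter is the Fisher test. Its null hypothesis is equal proportions, so it does not test a margin of 0.08 or 0.10. A large p-value could be misread as support for non-inferiority, and a small one as evidence against it.

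**Working it through.** **Plan's own figure.** Inputs from 3.3: success 0.95 in both arms, margin 0.08, one-sided alpha 0.05, power 90%, ratio 2:1.

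n_C = (1.645 + 1.282)² × (0.0475 + 0.0475/2) / 0.08² = 8.564 × 0.07125 / 0.0064 = 95.3, so 96 Control; twice 95.34 is 190.7, so 191 Cementless. Dividing by 1 - 0.25 (10% plus 15%) gives 254.7 and 128, that is 255/128 and 383 in total. The figures reproduce. The 10% allows for exclusions; it is not a design effect.

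**Assumptions.** The documents give no within-patient correlation (rho); I take 0.2 to 0.8. Section 3.5.2 bases the 10% on bilateral enrollment in an earlier study and does not say whether patients or knees are meant. If 10% of patients are bilateral, 0.2/1.1 = 18.2% of knees come from pairs. If 10% of knees are, the share is 10%.

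**Standard error.** The average multiplier is sqrt(1 + f × rho), where f is the share of knees in pairs:
- f = 18.2%: 1.018, 1.044 and 1.070 at rho 0.2, 0.5 and 0.8
- f = 10%: 1.010, 1.025 and 1.039

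**Alpha of the planned bound.** Exact enumeration: failures per arm are binomial for unilateral knees, convolved with pairs for which P(both fail) = q² + rho × q(1-q). Under the null hypothesis the Cementless failure rate exceeds the Control rate by the margin. Control success is 95% (planned) or 97.6% (from the 2.4% control failure rate cited in 3.3). Pairs with 10% of patients bilateral are 23/12 at 255/128, 20/10 at 217/109 (15% attrition) and 17/9 at 191/96.

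| Margin, knees | Independent: 95% / 97.6% | rho 0.2-0.8 at 95% | rho 0.2-0.8 at 97.6% |
|---|---|---|---|
| 0.08, 255/128 | 4.4% / 4.9% | 4.7-5.6% | 5.2-6.1% |
| 0.08, 217/109 | 4.4% / 5.1% | 4.7-5.6% | 5.4-6.3% |
| 0.08, 191/96 | 4.4% / 5.5% | 4.7-5.6% | 5.9-6.8% |
| 0.10, 255/128 | 4.6% / 5.0% | 4.9-5.8% | 5.3-6.2% |

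If 10% of knees are bilateral (13/6 pairs), margin 0.08 at 255/128 gives 4.6-5.1% and 5.1-5.6%. The success rates for margin 0.10 are assumed, since the plan gives none for that endpoint. At 95% success and margin 0.08, alpha reaches 5% near rho 0.4 with 10% of patients bilateral, and near rho 0.75 with 10% of knees.

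**A borderline case.** Failures 17/217 Cementless and 5/109 Control, that is 7.83% and 4.59%. The difference is 3.25 points and the planned standard error 2.71 points. The bound is 3.25 + 1.645 × 2.71 = 7.70, which meets 8. With the average multipliers it is 7.78, 7.90 and 8.02 at rho 0.2, 0.5 and 0.8. In two constructed data sets with these totals and 20/10 pairs, the clustered bound is:
- 8.38 (fails) if two Cementless pairs and one Control pair fail on both sides
- 7.82 (passes) if one Cementless pair fails on both sides and one pair per arm fails on one side

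**Fisher.** For the same totals the two-sided p is 0.35, although the planned rule is met. With 96/96 Control and 181/191 Cementless successes the rule is also met (bound 0.079), yet Fisher gives p = 0.034 against Cementless.

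**The case against.** The strongest reply is that 3.1.1 and 3.1.2 make pooling depend on the analyses in 3.1.5, which exist to deal with this correlation. A reader might infer that the poolability condition could not correct the error in any case. The documents do not support that. A gate requiring both the pooled and a patient-clustered bound to pass would give alpha of 4.3-4.5% at 95% success, and 4.9-5.0% at 97.6% for 255/128 and 217/109. A gate using a Breslow-Day test at 0.05, with fallback to unilateral patients, would give about 4.6-5.1% and 4.9-5.4% at 255/128. Both gates are assumptions. The plan specifies neither, and the unilateral/bilateral comparison in 3.5.6 is exploratory, with its 0.05 level stated for centers. So a gate might limit the error, but nothing in the text ensures it.

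Three further replies carry weight:
- At the planned 95% success the rule starts below 5%, and the excess needs a correlation that the documents do not give.
- The largest figures are not all due to clustering. At 191/96 and 97.6%, independent knees already give 5.5% because of the Wald approximation.
- Study success needs all four endpoints, so a reader who takes 6.8% as the study's false-success rate goes too far: these are upper limits for it.

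Pooling of knees is footnoted as agreed at a pre-submission meeting. That record is not in the documents, so whether this variance was accepted is unknown. The borderline example is chosen to lie near the margin; it shows that a decision can change, not how often. Fisher is supplementary, and the conclusion rests on the bound alone.

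**Conclusion.** The point holds in limited form. The standard error that decides two of the four co-primary endpoints omits within-patient correlation, although patients are the randomized unit and pairs lie within one arm. At 255/128, margin 0.08 and 10% of patients bilateral, rho of 0.2 to 0.8 raises single-endpoint alpha from 4.4% to 4.7-5.6% at 95% success, and from 4.9% to 5.2-6.1% at 97.6%. The size depends on the assumed correlation and bilateral share. The plan's 5% statement is therefore not assured for these endpoints, but the documents do not show that it fails.

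The missing poolability criterion is a lesser point of clarity. The Fisher wording is wrong but does not affect the decision. The change is worth making because it is cheap and corrects a deciding error bound.

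**What to change.** **Bound.** In 3.1.1, 3.1.2 and 3.2 keep the pooled knees and the point estimate, and compute the primary upper bound as (p_C - p_I) + 1.645 × SE. SE is the larger of the planned standard error and sqrt(V_C + V_I), with

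V_g = [G/(G-1)] × (sum over patients of the squared sum of (y - p_g) over that patient's knees) / n_g²

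where G is the number of patients and n_g the number of knees in arm g. Apart from G/(G-1), V_g is the robust variance by patient from GEE with identity link and working independence. The larger of the two is advisable because the robust variance is noisy with few pairs: at rho 0.2 and 95% success it fell below the planned variance in 22-25% of simulated trials. Report the independent-knee Wald bound as a sensitivity analysis and keep 3.1.5 (a) to (c).

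**Fisher.** Relabel it as a test of zero difference, or replace it with p = 1 - Phi((margin - (p_C - p_I)) / SE) at 0.08 and 0.10, using the same SE. This p is at most 0.05 exactly when the bound meets the margin.

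**Clarification.** State in 3.1.5 the poolability test, its level and which analysis is primary if it fails. With about 12 Control pairs such a test has little power, so the standard error should not depend on it.

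**Effect and cost.** In simulation (1,000,000 trials per case, margin 0.08, 10% of patients bilateral) the clustered bound has alpha of 4.4-4.5% at 95% success and 4.9-5.0% at 97.6% for 255/128. At 191/96 and 97.6% it still gives 5.3-5.4%. The standard error grows on average by about 1-7%. Power at 95% success, from rho 0.2 to 0.8, is 97.2-96.0% at 255/128, 94.8-93.0% at 217/109 and 92.9-90.1% at 191/96; the planned bound gives 97.3-96.7%, 95.4-94.5% and 93.7-92.8%. Taking the larger standard error leaves power unchanged to 0.1 point. The work is SAP wording and minor programming. The sponsor should confirm that the change fits the agency agreement footnoted in 3.1.1 and 3.1.2.

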3.1.2. ABSENCE OF REVSION/REMOVAL/UADE

Using a 10% margin of non-inferiority, the proportion of knees who are free of Revision/Removal/UADE during the course of the study in the Cementless group is non-inferior to the proportion of such knees in the Control group. The test is based on the upper bound of a one-sided 95% confidence interval for the difference, Control minus Cementless, of success proportions. A conclusion of non-inferiority is supported if the upper bound of the confidence interval is 0.10 or less. In addition, a Fisher's Exact p-value will also be computed to test this hypothesis.

^b Dmitrienko, Alex, et al. *Analysis of Clinical Trials Using SAS*. SAS Publishing, 2005, pp 75-76.

^c As agreed at FDA pre-submission meeting Q160425 April 13, 2016.

In this analysis, each knee will be considered as a separate case, and unilateral and bilateral subjects will be analyzed together, providing the unilateral and bilateral groups are poolable per sensitivity analyses given in Section 3.1.5^d.

3.1.3. KNEE SOCIETY ASSESSMENT (PAIN) SCORE

The mean Knee Society Assessment score (KSSA) for the Cementless group is non-inferior to the mean KSSA for the Control group using a 6.4-point margin of non-inferiority. This test will be based on the upper bound of a one-sided 95% confidence interval for the difference, Control minus Cementless, of means at 22+ months. A conclusion of non-inferiority is supported if the upper bound of the confidence interval is 6.4 or less.

3.1.4. KNEE SOCIEITY FUNCTION SCORE

The mean Knee Society Function score (KSSF) for the Cementless group is non-inferior to the mean KSSF for the Control group using a 9.2-point margin of non-inferiority. This test will be based on the upper bound of a one-sided 95% confidence interval for the difference, Control minus Cementless, of means at 22+ months. A conclusion of non-inferiority is supported if the upper bound of the confidence interval is 9.2 or less.

3.1.5. SENSITIVITY ANALYSES - UNILATERAL AND BILATERAL KNEES

To address the impact of possible correlation occurring due to including two knees from the same patient, for the two endpoints that will incorporate bilateral knees (Radiographic Success and Absence of Revision/Removal/UADE), additional sensitivity analysis will be conducted in order to address any potential correlation occurring due to including two knees from the same patient. These are to include:

- a. An analysis that considers only unilateral subjects.
- b. A repeated measures model approach that can account for possible correlation within subjects.
- c. An analysis of data at the patient level, in which a patient is considered a "failure" if either knee fails.

3.2. CALCULATION OF THE PRIMARY STUDY ENDPOINT

The confidence intervals used in the analysis of the binary primary endpoints (Radiographic Success and Absence of Revision/UADE) will be 1-sided, 95% confidence intervals for the difference between proportions in two independent samples. They will be calculated using the Wald method as based on a normal approximation to the binomial, as follows:

$$(p_C - p_I) + z_\alpha \sqrt{SE_C^2 + SE_I^2}$$

Where

^d As agreed at FDA pre-submission meeting **Q160425** April 13, 2016.

 p_C = proportion of success in the Control group,

p_I = proportion of success in the Investigational group,

 $\alpha = 0.05$, and

$$SE_C = \sqrt{\frac{p_C(1-p_C)}{n_C}}$$
 and $SE_I = \sqrt{\frac{p_I(1-p_I)}{n_I}}$

The confidence interval used in the analysis of the continuous primary endpoints (Knee Society Function and Assessment Scores) will be 95% confidence intervals for the difference between means in two independent samples. They will be calculated using the normal distribution, as follows:

$$(\bar{x}_C - \bar{x}_I) + z_\alpha \sqrt{\frac{s_C^2}{n_C} + \frac{s_I^2}{n_I}}$$

Where

 $\overline{x_C}$ = proportion of success in the Control group,

 $\overline{x_i}$ = proportion of success in the Investigational group,

 s_C = standard deviation for the Control group,

 s_{I} = standard deviation for the Investigational group,

and

 $\alpha = 0.05$

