3.3 SAMPLE SIZE JUSTIFICATION

In order to calculate the sample size for this study, the sample size needed to obtain 90% power for each primary endpoint was calculated. The endpoint requiring the largest sample size to maintain 90% power was Radiographic Success. Therefore, this is the sample size used in this study to ensure that we have a sufficient number of knees/patients to test each of the four primary endpoints with at least 90% power.

The sample size for the radiographic success primary endpoint was calculated as follows:

Let p_I and p_C denote the true population proportions of a successful outcome in the Cementless and Control groups, respectively.

Under H_0 , p_C is markedly larger than p_I and the Cementless device is inferior. Contrarily, under H_1 , this is not true and the true proportion of success for the Cementless device is, at worst, δ less than for the Control. We have δ = 0.08 (i.e., 8%).

Information about plausible values of the proportions p_I and p_C is available in the SSED for the LPS Flex Mobile Device (PMA #P060037). This document was used to help estimate the percentage of radiographic success for sample size purposes because it used a similar radiographic success/failure endpoint as the one given in this protocol. For purposes of the sample size calculation, we use the radiographic failure rates in Table 5 (page 18-19) of the document. This shows a 1.2% radiographic failure rate for the investigational device and a 2.4% radiographic failure rate for the control. Since we have slightly different radiographic success criteria, and because we want to ensure that we have adequate power for testing this endpoint, we will use 5% as our estimate of radiographic failure, giving a 95% estimate of radiographic success.

Assuming 95% to be the true, equal values of p_1 and p_2 , non-inferiority sample size calculations were implemented in nQuery Advisor 7.0 software using a 2:1 ratio of Cementless to Control subjects. This software uses methodology as described in an article by Farrington and Manning^e.

Definitions:

 p_l : Proportion of successes in the Experimental (Oxford Cementless) treatment group.

 $p_{\mathcal{C}}$: Proportion of success in the Control (Oxford Cemented) treatment group.

For a specified constant, $0 < \delta < 1$, the hypotheses of non-inferiority are:

$$H_0: p_C - p_I > \delta \text{ vs. } H_1: p_C - p_I \leq \delta.$$

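### The Wald bound that decides both binary co-primary endpoints exceeds its one-sided 5% error if control success is about 98-99% or higher

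*Combined protocol and SAP*

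**What the plan says.** Section 3.2 states that the intervals for the two binary co-primaries "will be 1-sided, 95% confidence intervals for the difference between proportions in two independent samples". It then fixes the method: "They will be calculated using the Wald method as based on a normal approximation to the binomial, as follows". The formula adds 1.645 standard errors to the observed difference, Control minus Cementless. Each arm's variance is computed from its own observed proportion, with no continuity correction and no rule for small failure counts.

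The bound alone decides each endpoint. For Radiographic Success (Section 3.1.1): "A conclusion of non-inferiority is supported if the upper bound of the confidence interval is 0.08 or less". For Absence of Revision/Removal/UADE (Section 3.1.2): "A conclusion of non-inferiority is supported if the upper bound of the confidence interval is 0.10 or less". Both sections also call for a Fisher's exact p-value, but only as an addition.

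Section 3.1 requires all four co-primaries to pass and concludes that "the type I error rate is preserved at 5% for the entire primary endpoint".

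Section 3.3 takes its planning rate from another device's published summary: "This shows a 1.2% radiographic failure rate for the investigational device and a 2.4% radiographic failure rate for the control". It then allows for more failures, "giving a 95% estimate of radiographic success". Of the sample size software it says: "This software uses methodology as described in an article by Farrington and Manning". No expected rate is given for revision, removal or UADE.

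**The concern.** A Wald bound needs enough failures in each arm for the observed variances to be reliable. Under 2:1 allocation the control arm is the smaller one. If control success is 99%, the chance of no failure among 96 control knees is 0.99^96 = 38%. The formula then sets the control standard error to zero and treats the control rate as known. The Cementless variance errs in the same direction: a sample good enough to pass shows a success rate above the null value, so its plug-in variance is smaller than the variance under the null.

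Both effects pull the bound down, so a device exactly at the margin is declared non-inferior too often. The argument in Section 3.1 for requiring all four endpoints is sound, but it delivers 5% only if each component test holds 5%.

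**Working it through.** **Inputs.** One-sided alpha 0.05 and the Wald formula (Section 3.2); margins 0.08 and 0.10 (Sections 3.1.1 and 3.1.2); planned success 95% in both arms, 2:1 allocation, 90% power, 191/96 evaluable and 255/128 enrolled knees (Section 3.3, Cementless/Control). For 15% attrition alone: 255 x 0.85 = 217 and 128 x 0.85 = 109. Control success from 95% to 100% is an assumed range; 97.6% is 100% minus the cited 2.4%.

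**The plan's sample size.** With unpooled variances, n_C = (1.645 + 1.282)^2 x 0.95 x 0.05 x (1 + 1/2) / 0.08^2 = 95.34, and twice that is 190.68. Rounded up, this is 96 and 191, exactly as stated. The Farrington-Manning formula with the null-restricted variance (null rates 0.9765 and 0.8965) gives 93.9 and 187.8, or 94 and 188, which is close. Dividing 191 and 96 by 0.75 gives 255 and 128.

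**Type I error.** Put the device exactly at the margin, p_I = p_C - margin. Enumerate every pair of failure counts, and sum the binomial probabilities of the pairs for which non-inferiority is declared. Do this for the Wald rule and for the Farrington-Manning score rule, which uses the variance estimated under the null.

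Each cell gives Wald / Farrington-Manning.

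| Margin | Control success | 191/96 | 217/109 | 255/128 |
|---|---|---|---|---|
| 8% | 95% | 4.4% / 5.1% | 4.4% / 5.2% | 4.4% / 5.0% |
| 8% | 97.6% | 5.5% / 5.2% | 5.1% / 4.9% | 4.9% / 4.8% |
| 8% | 98% | 5.9% / 5.1% | 5.3% / 4.8% | 5.0% / 4.9% |
| 8% | 99% | 7.5% / 4.8% | 5.5% / 4.7% | 6.0% / 4.9% |
| 8% | 100% | 9.6% / 5.4% | 6.5% / 3.6% | 8.1% / 4.9% |
| 10% | 95% | 4.4% / 4.9% | 4.5% / 5.3% | 4.6% / 5.1% |
| 10% | 99% | 6.5% / 5.0% | 5.9% / 4.7% | 5.5% / 4.8% |
| 10% | 100% | 8.3% / 4.9% | 7.5% / 4.5% | 6.7% / 4.2% |

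The pattern is not smooth in sample size because the counts are discrete. Over sizes between 191/96 and 255/128 with the 8% margin, the Wald error runs from 5.2% to 7.5% at 99% control success and from 6.0% to 9.7% at 100%. The score rule peaks at 5.4% at the three tabulated sizes. Over the sizes in between and control rates from 95% to 100%, it reaches at most 5.7%.

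**A result that changes.** Take 191/96, the 8% margin, no control failures and 10 Cementless failures.
- Wald: difference 10/191 = 0.0524; control standard error 0; Cementless standard error sqrt(0.0524 x 0.9476 / 191) = 0.0161; bound 0.0524 + 1.645 x 0.0161 = 0.0789. This passes.
- Score: null-restricted rates 1.00 and 0.92; standard error sqrt(0.92 x 0.08 / 191) = 0.0196; z = (0.0524 - 0.08) / 0.0196 = -1.41, short of -1.645. This fails.

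The score rule allows 9 Cementless failures here and Wald allows 10.

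**The case against.** **The high-success range may not arise.** Section 3.3 plans for 95% success, and Section 3.5.5 counts a knee revised before two years as a radiographic failure, which lowers radiographic success. At 95% the Wald rule is conservative. A reader might infer from the cited 1.2% and 2.4% failure rates that the plan's own source places the trial in the problem range. It does not: the error depends on control success, the source's control rate is 97.6%, and Wald is near nominal there. The 98.8% is the source's investigational arm. This stands, and it makes the point conditional.

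**The smallest size is the least favourable.** At 191/96 the whole allowance for attrition and non-poolable bilateral knees has been used up. At 217/109 the excess at 99% is small. But at 255/128 with the 8% margin it is 6.0%, so full enrolment without losses does not remove the excess.

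**Sizing method.** A reader might infer that the trial was sized with one test and will be decided by another. The text cites Farrington and Manning, but the unpooled formula reproduces 191/96 exactly and the score formula gives 188/94. The contrast rests on a citation alone, and it does not show the sample size to be wrong.

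**Study-wide error.** A reader might also infer that the 5% statement in Section 3.1 is shown to fail for the whole study. All four endpoints must pass, so the study-wide error comes near these figures only if the other three are almost certain to pass. The figures are upper limits.

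**Existing safeguards.** Appendix B promises more suitable tests if assumptions fail, and a Fisher's p-value is added. Neither replaces the deciding bound. Appendix B names no alternative interval and no trigger for these endpoints, so the choice could be made after the data are seen.

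**Conclusion.** The point holds in conditional form. If true control success is about 98-99% or higher, the Wald bound in Section 3.2 exceeds its nominal 5% for the endpoint concerned. At 99% the error is 5.5% to 7.5% with the 8% margin and 5.5% to 6.5% with the 10% margin at the three sizes examined. The 9.6% figure needs control success of exactly 100% at 191/96 and is an extreme.

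The arithmetic is firm. Whether control success will lie in that range is not known from the documents; for revision/removal/UADE, where no rate is given, near-100% success is an assumption. The calculation treats knees as independent; correlation between two knees of one patient is a separate matter, which Section 3.1.5 takes up. The practical consequence is limited to borderline results, where one knee can decide an endpoint.

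**What to change.** In Section 3.2, replace the Wald bound for both binary co-primaries with the Farrington-Manning test, or the Miettinen-Nurminen score upper bound, at one-sided 5%. Keep the margins of 0.08 and 0.10, and report the Wald bound as supportive. Make the change before treatment results are seen.

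The cost is SAP wording and standard software, with no added patients or data. For the 8% margin, exact power at 95% success in both arms moves from 94.1% to 93.0% at 191/96, from 95.7% to 95.1% at 217/109, and by less than 0.1 point at 255/128 (97.5% either way). All exceed the planned 90%. The Wald rule's slight conservatism at 95% success is given up: the error there rises from about 4.4% to 5.0-5.2% for the 8% margin. The score rule is itself approximate, as its peak of 5.4% at the tabulated sizes shows.
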